## 1 LIST OF ABBREVIATIONS AND DEFINITION OF TERMS

### 1.1 List of Abbreviations

Abbreviation	Definition
<, ≤, >, ≥	less than, less than or equal to, greater than, greater than or equal to
±	plus
Ac	acetylation
ADL	activities of daily living
AE	adverse event
ALP	alkaline phosphatase
ALT	alanine aminotransferase
AML	acute myeloid leukaemia
aPTT	activated partial thromboplastin time
AST	aspartate transaminase
BCR-ABL	breakpoint cluster region-Abelson
BUN	blood urea nitrogen
°C	degrees Centigrade
CALR	calreticulin
CBC	complete blood count
CD	cluster of differentiation
CFR	Code of Federal Regulations
cGMP	current Good Manufacturing Practices
CI	Clinical Improvement
CL/F	apparent total clearance of drug after oral administration
Clinical Benefit	not meeting progressive disease criteria as per Section 16.7 and safely tolerating IMG-7289
C min	minimum observed plasma concentration at 24 hours from last dose
CoREST	Co-repressor for RE1-silencing transcription factor
CR	complete remission or response
CXCL	chemokine (C-X-C Motif) ligand
CXCR4	chemokine (C-X-C motif) receptor 4
CT	computerized tomography
CTCAE	Common Terminology Criteria for Adverse Events
CV	co-efficient of variation
D	Day
DIC	Disseminated Intravascular Coagulation
DLT	dose limiting toxicity
DNA	deoxyribonucleic acid
DNMT	DNA-methyltransferase

Abbreviation	Definition
D pi	pharmacodynamic dose; the estimated dose of IMG-7289 needed in humans that provides sufficient exposure to inhibit normal haematopoiesis safely during a fraction of the 24-hour dosing cycle
D s	starting dose
DSMC	Data Safety Monitoring Committee
DSMP	Data Safety Monitoring Plan
ECOG	Eastern Cooperative Oncology Group
eCRF	electronic case report form
EFS	event free survival
ELN	European Leukaemia Network
EMH	extramedullary haematopoiesis
EOS	end of study
EOT	end of treatment
EPO	Erythropoietin
ESC	embryonic stem cell
ET	essential thrombocythaemia
FAD	flavine adenine dinucleotide
FPFV	first patient first visit
Free base of IMG-7289	N -[[(2 S )-5-[[[(1 R ,2 S )-2-(4-fluorophenyl)cyclopropyl]amino]-1-(4-methylpiperazin-1-yl)-1-oxopentan-2-yl]-4-(1 H -1,2,3-triazol-1-yl)benzamide, free base
FSH	follicle stimulating hormone
g or gm	Gram
g/dL	gram per deciliter
GCP	good clinical practice
G-CSF	gram colony stimulating factor
GFI1	growth factor independent 1 transcription factor
GFP	green fluorescent protein
GFR	glomerular filtration rate
GGT	gamma glutamyltransferase
GI	Gastrointestinal
GLP	good laboratory practice
GM-CSF	granulocyte-macrophage colony stimulating factor
GMP	Good Manufacturing Practices
H	Histone
HbF	foetal haemoglobin
HDAC	histone deacetylase
HED	human equivalent dose
HIV	human immunodeficiency virus

Abbreviation	Definition
HREC	Human Research Ethics Committee
HSC	haematopoietic stem cell
HSCT	haematopoietic stem cell transplant
IC	inhibitory concentration
ICH	International Conference on Harmonization
IEC	Independent Ethics Committee
IL	Interleukin
IMG-7289	N -[[ (2S) -5-[[ (1R,2S) -2-(4-fluorophenyl)cyclopropyl]amino]-1-(4-methylpiperazin-1-yl)-1-oxopentan-2-yl]-4-(1 H -1,2,3-triazol-1-yl)benzamide, bis-tosylate salt ; bomedemstat
indels	insertions and deletions
INR	International normalized ratio
IPF	immature platelet fraction
IRB	Institutional Review Board
IUD	intrauterine device
IWG-MRT	International Working Group for Myelofibrosis Research and Treatment
JAK	Janus Kinases
K	Lysine
KD	knockdown
KDM1A	lysine-specific demethylase 1
Kg	Kilogram
L	litre
LDH	lactate dehydrogenase
LIC	leukaemia initiating cell
LPLV	last patient last visit
LSD1	lysine-specific demethylase 1
LSDi	LSD1 inhibition or inhibitors
MAO; MAOI	monoamine oxidase(s); monoamine oxidase inhibitor(s)
MCH	mean cell haemoglobin
MCHC	mean cell haemoglobin concentration
MCV	mean cell volume
me; Me	methyl; methylation
Mg	Milligram
mg/kg	milligram per kilogram
mg/kg/d	milligram per kilogram per day
MedDRA	Medical Dictionary for Regulatory Activities
MF	Myelofibrosis

Abbreviation	Definition
mL	millilitre
mL/min	millilitres/minute
MPL	myeloproliferative leukaemia virus oncogene, thrombopoietin receptor
MPN	myeloproliferative neoplasias or neoplasms
MPP	multipotent progenitor
MPN-SAF TSS	Myeloproliferative Neoplasm Symptom Assessment Form Total Symptom Score
MPV	mean platelet volume
MRI	magnetic resonance imaging
mRNA	messenger RNA
Ms	milliseconds
MTD	maximally tolerated dose
MYB	V-Myb Avian Myeloblastosis Viral Oncogene Homolog
NCI	National Cancer Institute
ng·hr/mL	nanogram an hour per milliliter
nM	Nanomolar
NOAEL	no-observed-adverse-effect-level
NURD	nuclear remodeling and histone deacetylase
OCT4	octamer-binding transcription factor 4
OS	overall survival
PD	Pharmacodynamics
PE	physical examination
PET-MF	post-essential thrombocythaemia myelofibrosis
PFS	progression free survival
Ph	phosphorylation
PI	Principal Investigator (at each site responsible for patient care)
PISCF	Participant Information Sheet/Consent Form
PK	Pharmacokinetics
PKAP	Pharmacokinetic Analysis Plan
PMF	primary myelofibrosis
PPV-MF	post-polycythaemia vera myelofibrosis
PR	partial remission or response
PT	prothrombin time
PV	polycythaemia vera
QD	once daily
RBC	red blood cell
RDW	red cell distribution width
REST	RE-1 silencing transcription factor

Abbreviation	Definition
RNA	ribonucleic acid
SAE	serious adverse event
SAP	Statistical Analysis Plan
SD	standard deviation
Sh	short hairpin
SOA	schedule of assessments
SOC	standard-of-care
SOX2	see SRY
SRM	Study Reference Manual
SRY	(sex determining region Y)-box 2; also known as SOX2
STAT	Signal Transducer and Activator of Transcription
T max	time to maximum concentration
TCP	Tranylcypromine
TF	transcription factor
TNF	tumour necrosis factor
TPO	Thrombopoietin
μL	Microliter
μM	Micromolar
Ub	ubiquitination
VAF	variant allele frequency
V z /F	apparent volume of distribution during terminal phase after oral administration
WBC	white blood cell
WHO	World Health Organization
WOCBP	women of child-bearing potential

## 2 PROTOCOL SYNOPSIS

Protocol Title: A Multi-Center, Open Label Study to Assess the Safety, Steady-State Pharmacokinetics and Pharmacodynamics of IMG-7289 in Patients with Myelofibrosis
Protocol No: IMG-7289-CTP-102
Investigator/Study Centers: Approximately 25 sites in Australia, Germany, Italy, UK and US with additional sites and countries as needed.
Study Objectives:  Hypothesis: IMG-7289 (bomedemstat) is a safe and tolerable orally available agent when administered to patients with myelofibrosis including primary myelofibrosis (PMF), post-polycythaemia vera myelofibrosis (PPV-MF), and post-essential thrombocythaemia myelofibrosis (PET-MF) (collectively referred to as 'MF'); inhibition of lysine-specific demethylase 1 (LSD1) by IMG-7289 will reduce spleen size in those with splenomegaly, improve haematopoiesis and reduce constitutional symptoms associated with these disorders.  Primary Objectives: To evaluate in MF patients the effect of IMG-7289 on: 

• Safety and tolerability

• Pharmacokinetics (Phase 1/2a only)

• Reduction in spleen volume

 Exploratory Objectivesφ: To evaluate in MF patients treated with IMG-7289: 

• The adequacy of the treatment regimen in producing a pharmacodynamic effect

• Haematologic response*

• Improvement in constitutional symptoms assessed using the Myeloproliferative Neoplasm Symptom Assessment Form (MPN-SAF; Phase 1/2a only) and the MPN-SAF TSS (Total Symptom Score; Phase 2b)

• Reduction in bone marrow fibrosis score

• Relationship between dose and plasma trough concentrations over time (Phase 1/2a only)

• The impact of therapy on disease burden as measured by malignant-cell specific nucleic markers (DNA or RNA)**

• The effect of treatment on cytokine profiles***

• The relationship between genetic aberrations in malignant cells and pharmacodynamic response

• To correlate conventional clinical responses with exploratory assessments of response

 <small>*Haematologic parameters, all of which may be assessed during treatment or after drug has been discontinued for a specified interval, may comprise: complete blood count (CBC) including platelets, red and white blood cell (RBC and WBC) and circulating blast cell counts; cellular composition of the bone marrow (% blasts); and, the induction of foetal haemoglobin. **Nucleic markers include RNA and/or DNA mutations detected by sequencing or other nucleic assay methods. ***Cytokine quantification. φSome or all may be analysed time and cost permitting.</small>
Investigational Drug: The active drug substance is identified as IMG-7289 (bomedemstat). IMG-7289 is an irreversible inhibitor of LSD1. CCI [REDACTED] [REDACTED] [REDACTED]
IMG-7289 will be supplied as capsules in multiple strengths. These strengths, based on IMG-7289 free base, i.e., the active substance, may include: CCI [REDACTED] Capsule strengths

provided may change throughout the duration of the study. Such details will be included *via* updates to the Pharmacy Manual.

**Study Population:** Approximately seventy-five (75) patients eighteen years of age or older with intermediate-1, -2 or high risk PMF, PPV-MF, PET-MF (referred to collectively as 'MF') will be treated.

**Methodology:** This is a multi-center, open-label study evaluating the safety, tolerability, steady-state pharmacokinetics and pharmacodynamics of IMG-7289 administered orally once daily in patients with myelofibrosis (MF).

The therapeutic goal for the treatment of MF is to inhibit the activity of LSD1 in haematopoietic cells, particularly megakaryocytes, for only a fraction of the 24-hour dosing cycle, sufficient to reduce platelets to a safe level while inhibiting to the greatest extent possible the production, by megakaryocytes, of cytokines and growth factors that drive bone marrow fibrogenesis and symptoms. Considerations for a safe and therapeutic starting dose included chronic toxicology studies, in conjunction with the clinical experience of the patients who have received IMG-7289 to date in both IMG-7289-CTP-101 and -102. In the CTP-101 study, IMG-7289 was administered to patients with high-risk AML and MDS; the therapeutic thesis was to completely inhibit LSD1 in all haematopoietic cells, targeting both leukaemic stem cells and blasts, recognizing that patients would need clinical support for cytopenias. The starting dose was 0.75 mg/kg/d and the effective dose, at which no safety signals were observed, was deemed 6.0 mg/kg/d. Though the great majority of the patients entered the study with Grade 3/4 thrombocytopenia, patients at all dose levels of IMG-7289 required platelet transfusions. This sensitivity of thrombopoiesis to LSD1 inhibition in high-risk AML/MDS patients reflects the generally compromised nature of the bone marrow, including the reduction of megakaryocytes, in that disease.

Taking this observation into account in association with the therapeutic goal for the treatment of myeloproliferative neoplasms - inhibiting LSD1 activity in haematopoietic cells for only a *fraction* of the 24-hour dosing cycle - and PK modeling, a starting dose ( $D_s$ ) of 0.25 mg/kg/d was selected for the Phase 1/2a portion of this study. CCI [REDACTED]

[REDACTED] A dose-response curve was subsequently generated that provided a titration algorithm to adjust dose to achieve the modified target platelet count of between 50-75 k/ $\mu$ L (50-75 x 10^9/L), devised with a view to minimizing the probability of severe thrombocytopenia. CCI [REDACTED]

[REDACTED] Accordingly, to enable patients to more quickly reach the optimum dose while still maintaining an adequate safety margin, a new IMG-7289 starting dose of 0.5 mg/kg QD was selected with protocol Amendment 4. With continued observation of additional patients treated, the estimated optimal dose for most patients ranges between 0.6 and 0.8 mg/kg/d. Thus, a new starting dose of 0.6 mg/kg/d has been chosen, CCI [REDACTED]

[REDACTED] Starting therapy at a dose closer to the optimal dose should accelerate the process of symptom and spleen volume reduction. Additional detail for the rationale on the dose and dose schedule can be found in Section 3.6.

CCI

### Study Conduct

This study initiated as a Phase 1/2a study assessing the safety of the starting dose, an 85 day duration of treatment, and the pharmacokinetic and pharmacodynamic effects of IMG-7289, with transition to a Phase 2b study incorporating changes supported by the Phase 1/2a data. This study consists of two treatment periods: the Initial Treatment Period (ITP), followed by the Additional Treatment Period (ATP). Patients are now enrolling in the Phase 2b portion of the study, in which patients are treated daily for 169 days in the ITP. The ATP offers treatment to qualifying patients for an additional 169 days.

During the ITP, patients will return for study assessments weekly for 8 weeks CCI

For the exceptional patient whose dose has not stabilized, weekly visits may continue at the PI's discretion (note: bi-weekly visits may also continue post Day 112). CCI

Such patients qualify for entry into the ATP, a transition which should occur without interruption in dosing. Patients not deriving clinical benefit, or who achieve complete response (CR), partial response (PR) or clinical improvement (CI) and subsequently relapse (Section 16.7) the equivalent of treatment failures, will discontinue IMG-7289 and undergo End of Treatment (EoT), pre-End of Study (pre-EoS) and End of Study (EoS) visits.

In the ATP, treatment may continue for an additional 169 days in those patients deriving clinical benefit, as determined by the Principal Investigator. Qualifying patients will return for study assessments monthly CCI It is anticipated that patients continuing in the ATP will have already achieved a stable dose, with bi-weekly visits no longer necessary. For the exceptional patient whose dose has not stabilized, bi-weekly visits may continue at the PI's discretion. On Day 168, patients will undergo the same procedures and assessments as in the ITP, including MRI or CT (if the patient is not a candidate for MRI), and bone marrow sampling. Prior to or at the CCI a 'qualification'

assessment will be made to determine whether the patient is continuing to derive clinical benefit. Such patients thereby qualify for re-entry into the ATP, which is iterative; patients may continue to receive IMG-7289 for as long as they continue to qualify.

**Note:** In Germany, use of computerised tomography (CT) is not permitted for patients unable to undergo magnetic resonance imaging (MRI). Only MRI is permitted for study purposes.

All patients will undergo follow-up period visits, including an EoT visit on the day of last dose or as soon as possible thereafter, a pre-EoS visit approximately 14 days post last dose, and an EoS visit approximately 28 days post last dose. Patients that do not enter the ATP, or discontinue early, will enter the follow-up period beginning with an EoT.

Patients will be followed closely throughout the study for both Adverse Events (AEs) and signs of toxicity by frequent monitoring of clinical signs and symptoms and by peripheral blood and urine analyses. Pharmacodynamic effects will be closely monitored by frequent haematology assessments of peripheral blood, and requisite bone marrow aspirates and biopsies. Throughout dosing, transfusions may be administered if needed in accordance with standard institutional guidelines.

#### IMG-7289 Dosing

Through the use of dose titration, all patients will be dosed to the estimated dose of IMG-7289 needed in humans that provides sufficient exposure to inhibit normal haematopoiesis safely for a fraction of the 24-hour dosing cycle (designated the  $D_{pi}$ ).

#### *Initial Treatment Period (ITP):*

**Note:** Please refer to Section 7.2.3.1 for patients currently being treated under Amendment 5

For patients commencing treatment under Amendment 6, treatment will begin on Day 0 at the new  $D_s$  of 0.6 mg/kg QD. In association with this increased starting dose, the first up-titration is not permitted until Day 28. Extending the time to first up-titration from Day 14 to Day 28 is supported by the observation that the time needed to reach a stable platelet count is between 3 and 4 weeks; additionally, this approach minimizes the risk of severe thrombocytopenia for the few patients who may require less than 0.6 mg/kg/dCCI

[REDACTED]

The platelet titration target expected to be associated with a clinically significant therapeutic effect is:

- A platelet count of  $\geq 50$  to  $\leq 75$  k/ $\mu$ L ( $50-75 \times 10^9/L$ ).

Please refer to Section 7.2.3.2 for additional information on the dosing of Amendment 6 patients.

*Additional Treatment Period (ATP):* Qualifying patients will 're-start' IMG-7289 on ATP Day 0, with dose titration continuing as *per* the Titration Rules in **Table 3**; there should be no interruption in dosing (i.e., Day 168 = Day 0 of new ATP). Additional dose-titration may occur in consultation with the Medical Monitor.

**Study Duration:** CCI

the anticipated duration of participation in the study is expected to be at least 32 weeks from first patient-first visit (FPFV) to last patient-last visit (LPLV). Additional treatment may be given, contingent on an assessment of patient benefit.

**Study Assessments:** The assessments outlined below are presented in detail by study visit in Section 9, and in the Schedule of Assessments Sections 16.1).

The Myeloproliferative Neoplasm Symptom Assessment Form Total Symptom Score (MPN-SAF TSS) will be used. The 24-HOUR RECALL tool (Appendix 16.8) will be completed daily for the 7 days preceding first dose (Days -6 to pre-dose Day 0) during Baseline. The 7-DAY RECALL tool will be completed weekly from Day 7 through the EoS Visit (Appendix 16.9). Multiple questionnaires will need to be provided to patient for completion between visits as visit schedule decreases over time.

Adverse events (AEs) will be assessed at every visit post first IMG-7289 dose through the EoS visit.

**Note:** In the UK, serious AEs (SAEs) will be recorded from time of consent through the EoS **or** until the Investigator and Imago BioSciences determine follow-up is no longer necessary.

Physical Examinations (PE), including vital signs: a **Full Physical Exam** will be performed at Screening. **Limited Physical Exams (LPE)** will be performed at all other clinic visits throughout the study. LPEs include weight, a review of body systems to assess change from previous PE, and spleen measurement. The edge of the spleen shall be determined by palpation, measured in centimeters, using a soft ruler/tape, from the costal margin to the point of greatest splenic protrusion. The spleen should be measured in the same manner at all visits.

Urine or serum pregnancy testing will be performed for women of child-bearing potential (WOCBP; defined in Section 6.1 ) at Screening, Baseline (if separate from Screening visit), pre-dose Day 0, monthly (i.e., Days 28, 56, 84, 112, 140 and 168) throughout the study, upon suspicion of relapse, at the EoT, pre-EoS, and EoS/ET visits and if pregnancy is suspected while the patient remains on-study.

Bone marrow aspirate\* and biopsy will be performed\*\*:

- At Baseline (no more than 21 days prior to the first IMG-7289 dose).
- At Day 168 ( $\pm 7$  days).
- Approximately every 6 months thereafter, at Day 168 ( $\pm 7$  days) of the ATP, for as long as the patient continues to qualify.
- At EoT and ET (unless performed within the prior 5 weeks), and upon suspicion of relapse (unless performed in the last 21 days or is scheduled in the next 7 days).

\*Aspirate from the first pull whenever possible, but no later than the second pull, is required.

\*\*The total number of bone marrow evaluations required during the ITP is 2 in ~32 weeks. Additional marrow evaluation is required only if the patient qualifies for the ATP, demonstrates response followed by suspected relapse, or evidence of progressive disease.

MRI or CT (if the patient is not a candidate for MRI) of the abdomen will be performed.

- Pre-dose Day 0 ( $\pm 2$  days)
- At the Day 84 and Day 168 visits ( $\pm 7$  days)
- Approximately every 6 months thereafter, at Day 168 ( $\pm 7$  days) of the ATP, for as long as the patient continues to qualify

- At EoT, ET, and upon suspicion of relapse (unless performed within the prior 5 weeks)

**Note:** In Germany, use of computerised tomography (CT) is not permitted for patients unable to undergo magnetic resonance imaging (MRI). Only MRI is permitted for study purposes.

Clinical laboratory measures: The following laboratory measures will be performed at Screening, Baseline (if separate from Screening visit), pre-dose Day 0, upon suspicion of relapse, at the EoT, pre-EoS, and EoS/ET visits, and in accordance with the below:

- Biochemistry – monthly (i.e., Days 28, 56, 84, 112, 140 and 168) throughout the study
- Haematology – every clinic visit throughout the study
- Coagulation – monthly (i.e., Days 28, 56, 84, 112, 140 and 168) throughout the study
- Urinalysis – Day 84 and Day 168 throughout the study

CCI [REDACTED] Sample collection time-points are below.

- Pre-dose Day 0, Days 14, 28, 84 and 168, and each Day 168 visit of the ATP, for as long as the patient continues to qualify
- At EoT, and at ET (ET required only if the patient discontinues during the ITP)

Red Cell Haemoglobin F (HbF) and %F cells (Selected sites only/ITP only):

- Pre-dose Day 0, Day 84 and Day 168
- At EoT and ET (both required only if the patient discontinues during the ITP)

CCI [REDACTED]

\*Any bone marrow aspirate samples will undergo genomic analysis as per the bone marrow sampling schedule.

CCI [REDACTED]

Blood, bone marrow and/or their contents may be retained for future exploratory studies.

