### 9.2 Screening Period, Including Baseline and Enrollment

The Screening period is comprised by Screening and Baseline visits which may be performed on the same day; in this circumstance, the visit must be completed within 21 days before Day 0. If the patient screen fails, document the reason(s) in the source data and on the Screening & Enrollment log.

Adverse events (AEs) will be assessed at every visit. Events occurring pre-first IMG-7289 dose will be recorded as Medical History; those occurring post first IMG-7289 dose through the EoS visit will be recorded as AEs.

**Note:** In the UK, serious AEs (SAEs) will be recorded from time of consent through the EoS **or** until the Investigator and Imago BioSciences determine that follow-up is no longer necessary.

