## 11.2 Adverse Events

The Investigator is responsible for monitoring the safety of patients who have enrolled in the study and for accurately documenting and reporting information as described in this section. Patients will be instructed to report to the Investigator any AE that they experience. Investigators will ask about the occurrence of AEs at each visit. Investigators are required to document all AEs occurring during the clinical study, commencing with the first dose of IMG-7289 through to the End of Study Visit (scheduled at 28 days post last IMG-7289 dose). Adverse event recording will continue for patients who discontinue study treatment early but remain in follow-up, until their End of Treatment, Pre-End of Study and End of Study Visits have been completed.

Note: Any medical event which occurs from the time of Informed Consent but prior to dosing with IMG-7289 must still be documented in the patient's medical notes and will be recorded on the appropriate medical history eCRF pages.

**Note:** In the UK, serious AEs (SAEs) will be recorded from time of consent through the EoS or until the Investigator and Imago BioSciences determine that follow-up is no longer necessary.

Adverse events will be recorded on designated eCRF pages. Each AE is to be characterised (i.e., verbatim term) and information provided regarding its seriousness, start and stop dates, intensity, outcome, and causal relationship with the study drug.

An AE is any undesirable physical, psychological or behavioral effect experienced by a patient during participation in an investigational study, in conjunction with the use of the drug or biologic, whether or not product-related. This includes any untoward signs or symptoms experienced by the patient from the time of first dose with IMG-7289 until completion of the study.

Adverse events may include, but are not limited to:

- Subjective or objective symptoms spontaneously offered by the patient and/or observed by the Investigator or medical staff
- Findings at physical examinations
- Laboratory abnormalities of clinical significance

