### 11.2.3 Serious Adverse Events

Serious adverse events will be reportable from the time the time of first dose through the End of Study Visit (scheduled for approximately 28 days post last IMG-7289 dose) or until the Investigator and Imago BioSciences determine that follow-up is no longer necessary. Serious adverse events that are suspected to be drug related will be reported even if they occur when the patient is no longer on the study.

**Note:** In the UK, serious AEs (SAEs) will be recorded from time of consent through the EoS or until the Investigator and Imago BioSciences determine that follow-up is no longer necessary.

An SAE is any AE that results in any of the following outcomes:

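### Outside the UK, a serious non-fatal complication of the mandatory baseline marrow biopsy, or of another study procedure between consent and first dose, is recorded as medical history and not reported to the sponsor as an SAE

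*Protocol*

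**What the plan says.** The general rule appears in several places and is consistent.

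- **Synopsis, Study Assessments:** "Adverse events (AEs) will be assessed at every visit post first IMG-7289 dose through the EoS visit".
- **Section 9.2:** "Events occurring pre-first IMG-7289 dose will be recorded as Medical History". No exception is made for events that are serious or caused by a study procedure.
- **Section 11.2, duty to document:** "Any medical event which occurs from the time of Informed Consent but prior to dosing with IMG-7289 must still be documented". The place is the patient's notes and the history forms: these events "will be recorded on the appropriate medical history eCRF pages".
- **Section 11.2, definition of an AE:** "This includes any untoward signs or symptoms experienced by the patient from the time of first dose with IMG-7289 until completion of the study".
- **Section 11.2.3:** "An SAE is any AE that results in any of the following outcomes", and "Serious adverse events will be reportable from the time the time of first dose through the End of Study Visit".

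The exception is a country note repeated in the Synopsis and in Sections 9.2, 11.2 and 11.2.3: "In the UK, serious AEs (SAEs) will be recorded from time of consent through the EoS".

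The protocol also places study procedures inside the uncovered interval. Written consent comes before any study procedure (Section 9.1). Marrow aspirate and biopsy are required at Baseline, Day -21 to Day -1 (Section 9.2.2), within a Screening period that opens at Day -28 (Section 9.2.1).

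**The concern.** A marrow aspirate and trephine biopsy is an invasive procedure, and here the protocol requires it of every patient. If it causes a serious bleed or an infection needing admission before Day 0, the harm comes from taking part in the trial, whatever the drug later does. The sponsor should hear of it quickly and in a form that marks it as serious.

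As written, only UK sites have an instruction that leads there. Elsewhere the event becomes a history entry with no seriousness classification and no reporting deadline. The same complication is thus handled in two ways within one trial, according to country. At stake are the sponsor's timely knowledge of procedural harm and a complete record of it, not the estimate of drug toxicity.

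**Working it through.** The protocol gives no figure to reproduce and the point rests on no calculation. The check is whether the passages, read together, leave a route by which a pre-dose serious event outside the UK reaches the sponsor as an SAE.

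1. **Can the event be an AE?** Section 11.2 starts its description of untoward signs and symptoms at first dose, and Section 9.2 sends anything before that to medical history. Section 9.2 also says AEs are assessed at every visit, which is wider than the Synopsis sentence, but both leave pre-dose events outside the AE record.
2. **Can it be an SAE without being an AE?** No. Section 11.2.3 defines an SAE as an AE with a listed outcome, and separately starts the reportable window at first dose.
3. **Does the 24-hour report apply?** Section 11.2.4 requires it once the investigator finds that the event meets the protocol definition of an SAE, regardless of relationship to drug. From step 2, a pre-dose event outside the UK does not meet that definition. The UK note speaks of recording. I read it, from its place in Section 11.2.3, as carrying the 24-hour duty too.
4. **Does a mandated procedure fall in the gap?** Yes. Consent precedes procedures (9.1) and the marrow precedes dosing (9.2.2). Blood sampling before dosing falls there too, as does the Day 0 abdominal scan when it is done before dosing.
5. **How long is the gap?** Up to 28 days for Screening (Day -28 to Day -1) and up to 21 for the marrow. If Screening and Baseline are combined, Section 9.2 requires that visit within 21 days before Day 0.
6. **Where does it apply?** The Synopsis names Australia, Germany, Italy, the UK and the US: 5 - 1 = 4 of the named countries follow the first-dose rule.
7. **What of patients never dosed?** Section 9.2.3 enrols patients after the Screening and Baseline procedures, and Section 14.4 provides case report forms for enrolled patients. For a screen failure, Section 9.2 asks for the reason in the source data and on the screening log. A patient harmed by the biopsy and then not enrolled may therefore not reach the database at all, even as medical history.
8. **Does the SAP pick it up?** SAP Section VI.D repeats capture from first dose, Section VII.A lists medical history, and Section IX.B expects every reported AE to be treatment-emergent. The visible text has no place for pre-dose SAEs, including those the UK note will generate. Parts of the SAP are redacted and the table shells are a separate document.

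**The case against.** The strongest reply is that this is a deliberate and consistently stated choice. Starting AE capture at first dose keeps the safety data about the drug, and a country note is not a contradiction. Pre-dose events are not ignored: Section 11.2 requires them in the notes and on history pages, and Section 9.3.1.1 updates the history and rechecks eligibility before dosing. Section 11.2.4 requires immediate report of a death during the study, without tying this to first dose, which may well cover a pre-dose death.

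Much of this stands. Deaths have their own route, and in enrolled patients other events are documented. The on-treatment safety analysis is also sound: the Safety population consists of dosed patients (SAP Section VI.K), and Section IX.B restricts AEs to on-treatment onset with a programmatic check if needed. What the reply does not supply is a 24-hour report for a serious non-fatal procedural event. A wish to isolate drug effects is a reason to tabulate such events apart, not to leave them unreported.

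Four stronger readings are tempting and go beyond the documents.

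- **Withdrawal of earlier therapy.** A reader might infer that all harm from stopping MPN treatment is lost too, and that every patient is exposed to it. Inclusion criterion 10 counts the 2 weeks (4 for interferon) back from Day 0, not from consent, so part or all may precede consent, where the UK rule would not reach either. Criterion 4 admits patients intolerant of, or not candidates for, approved therapy, so some may have nothing to stop. Section 11.2.3 also excludes hospitalisation consistent with progression, which may take in some admissions for recurrent disease.
- **Committee review.** A reader might infer that the DSMC/SAB never sees these events. Section 8.1 gives it safety parameters under a separate plan that is not available here.
- **Regulatory expedited reporting.** Section 11.2.2 classes events for regulators by relationship to study drug, and the regional criteria are not given. Only the loss of the site-to-sponsor report is shown.
- **A probability of at least one event.** One could apply an assumed rate to all 75 patients. The documents give no rate, and the 75 include UK patients and patients already dosed (18 in Phase 1/2a alone, SAP Section IV.C).

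**Conclusion.** The concern holds for serious, non-fatal complications of study procedures done after consent and before first dose, above all the mandatory baseline marrow. Outside the UK these are medical history by rule and carry no 24-hour SAE report. The biopsy part is unconditional. Withdrawal of therapy counts only where it happens after consent and the event is not attributed to progression.

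The size can be stated only as exposure: one required marrow procedure per patient, an interval of up to 28 days (21 for the marrow), and four of five named countries. The share of patients outside the UK is not given, and additional countries are allowed for. No expected count should be attached.

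The conclusion assumes that the Study Reference Manual, which holds the detailed SAE procedure and is not available here, adds no wider duty. If it does, the protocol text should still be brought into line with it. This is a patient-safety gap worth closing at the next amendment. It is not a threat to the primary safety results.

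**What to change.** In the Synopsis and in Sections 9.2, 11.2 and 11.2.3, apply the existing UK rule in all countries, so that SAEs are recorded and reported from consent. If the sponsor wants something narrower, the minimum is SAEs related to a protocol-mandated procedure and, where it occurs after consent, to protocol-required withdrawal of therapy. State that the rule covers patients who fail screening, and say where their events are recorded, since Section 14.4 provides forms only for enrolled patients.

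In the SAP, bring Sections VI.D and IX.B into line and add a listing of pre-dose SAEs separate from treatment-emergent events. Summaries of on-drug events then stay as planned, and the UK's pre-dose SAEs also gain a defined place.

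The cost is protocol and SAP wording and a few extra SAE forms. The sponsor already provides for consent-onward recording in the UK. The change can help only patients still to be consented.
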